11.5.3 Fitting Characteristics – Actual versus Theoretical

The fitting characteristics will be analysed separately for tightness and corneal overlap using linear mixed models. The regression models will include the experimental design factors: lens type, period, and the lens by period interaction as fixed effects, and subject as a random effect. Comparisons will be carried out using 95% confidence intervals constructed of least-square means (LSM) from the linear mixed models.

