3 STUDY DESIGN & RATIONALE

This will be a one-day, double-masked, randomised, repeated measures study. Each subject will wear the three lens types (Acuvue® OASYS® with HydraClear Plus™ in two base curves and 1-Day Oasys with HydraLuxe™ in one base curve). A total of six lenses will therefore be worn by each subject (3 per eye).

An attempt will be made to include subjects who have large corneas or have previously demonstrated loose / tight fitting contact lenses since eyes with larger corneas tend to be less successful in contact lens fitting.

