3.1 Randomisation

Subjects will wear each of the three lens types bilaterally in random succession. A random number generator (Microsoft Excel) will determine the randomisation of lenses to subjects, which is then incorporated into the Randomisation Log.

The randomised assignment of subjects will be performed at the first assessment prior to the first randomised lens fitting. The following must be ensured prior to randomisation:

- Informed consent has been obtained
- Subjects meet all inclusion / exclusion criteria
- Subject history and baseline information have been collected

Subjects who are discontinued may be replaced in order to achieve the targeted minimum number of cohort subjects, but the ID number will not be reused.

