4 INVESTIGATIONAL SITES

4.1 Number of Sites

Two investigational sites in the UK: Visioncare Research Clinic, Farnham: Aston University Research Clinic, Birmingham

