11.5 Statistical Analysis

11.5.1 Success Rates – Two Designs versus One Design

Fit acceptance (0=Unacceptable, 1=Acceptable) will be analysed using a generalized linear mixed model with a binary distribution and a logit link function. Lens type will be included as a fixed effect and subject will be included as a random effect.

If the incidence rate is too low or there are problems with the convergence of the above model, the method of Wilson⁵ will be used to evaluate the confidence intervals.

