11.5.2 Success Rates – Actual versus Theoretical

Fit acceptance (0=Unacceptable, 1=Acceptable) will be analysed using a generalized linear mixed model with a binary distribution and a logit link function. Lens type, period, and the lens by period interaction will be included as fixed effects and subject will be included as a random effect. The proportion of eyes with acceptable lens fit with each lens type will be calculated with 95% confidence intervals. These confidence intervals will be compared to the theoretical success rates.

If the incidence rate is too low or there are problems with the convergence of the above model, the method of Wilson⁵ will be used to evaluate the confidence intervals.

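### Sections 11.5.1 to 11.5.3 model two eyes by three lenses with a single subject random effect, so interval widths are wrong in a direction the protocol does not let one determine

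*Protocol*

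**What the plan says.** Protocol Section 3.1 allocates lenses by subject and period: "Subjects will wear each of the three lens types bilaterally in random succession". Section 3 counts three lenses on each of two eyes, six readings per subject.

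The models are written out in the protocol:
- Section 11.5.1: "Lens type will be included as a fixed effect and subject will be included as a random effect".
- Section 11.5.2: "Lens type, period, and the lens by period interaction will be included as fixed effects and subject will be included as a random effect".
- Section 11.5.3: lens type, period and their interaction as fixed effects, "and subject as a random effect".

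The unit of analysis in Section 11.5.2 is the eye: "The proportion of eyes with acceptable lens fit with each lens type will be calculated with 95% confidence intervals". Section 11.5.1 uses the same binary response and names no other unit. If the logistic model fails, both sections fall back on Wilson intervals, with no adjustment for paired eyes. Section 11.2 undertakes to hold the overall type I error at 5%.

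**The concern.** A single subject intercept gives every pair of a subject's six readings the same correlation. The design does not. Two eyes wearing the same lens share lens, period and grading session, and the same eye recurs across the three lenses. Two variance terms are therefore missing: subject-by-lens (the same as subject-by-period here, since one lens fills each period) and eye within subject. The fixed lens-by-period interaction in 11.5.2 and 11.5.3 does not supply either; it describes means, not variation between subjects.

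Omitting the first term treats the second eye as an independent replicate of the lens allocation and makes lens contrasts look too precise. Omitting the second puts eye-to-eye differences into the residual and makes them look too imprecise.

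Subject-by-lens variation is not far-fetched. The introduction and hypothesis i presuppose that different eyes suit different designs, and the sample enrolment log records large HVID or corneal diameter once per subject. That makes it plausible that the lens-specific response is partly shared by the two eyes, though the protocol does not show how far. At stake is whether the intervals in Section 11.5 have their stated coverage.

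**Working it through.** **The plan's own figure.** Section 11.1 gives an 80% interval of ±5.0% for 60 subjects at 90% success. 1.2816 × sqrt(0.9 × 0.1 / 60) = 0.0496, which agrees. With 120 independent eyes it would be 1.2816 × sqrt(0.09 / 120) = 0.0351. So this planning figure counts subjects, whereas the analysis in 11.5.2 counts eyes.

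**Inputs.** N = 60 subjects, 2 eyes, 3 lenses (Sections 3 and 11.1). Variances: vs (subject), ve (eye within subject), vsl (subject-by-lens), s2 (residual). The protocol gives none of these, so all splits below are assumptions. The algebra is for a balanced linear model with lens as the only fixed effect.

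**Between-lens contrast.** The five within-subject degrees of freedom have expected mean squares s2 + 3ve (1 df), s2 + 2vsl (2 df) and s2 (2 df). The subject-only model pools them: s2 + 0.6ve + 0.8vsl.
- Variance the planned model reports: (s2 + 0.8vsl + 0.6ve)/N.
- True variance: (s2 + 2vsl)/N.
- They are equal only when 1.2vsl = 0.6ve, that is vsl = ve/2.

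With ve = 0 and r = vsl/(vsl + s2), true/reported = (1 + r)/(1 − 0.2r).
- r = 0.3: 1.3/0.94 = 1.383; SE too small by a factor 1.18; type I error 2[1 − Φ(1.96/1.176)] = 9.6%.
- r = 0.5: 1.5/0.9 = 1.667; factor 1.29; type I error 12.9%.

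On the tightness scale, take the SD of 10 in the sample size table as a per-eye paired difference (an assumption). Then 2(s2 + vsl) = 100, so s2 + vsl = 50:

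| r | ve | true SE | reported SE | type I error |
|---|---|---|---|---|
| 0 | 0 | 0.913 | 0.913 | 5.0% |
| 0.25 | 0 | 1.021 | 0.890 | 8.8% |
| 0.5 | 0 | 1.118 | 0.866 | 12.9% |
| 0.9 | 0 | 1.258 | 0.827 | 19.8% |
| 0.5 | 50 | 1.118 | 1.118 | 5.0% |
| 0 | 50 | 0.913 | 1.155 | 1.3% |
| 0.5 | 100 | 1.118 | 1.323 | 2.0% |

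The far end of the assumed range on the conservative side (r = 0, ve = 100) gives 0.4%.

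Simulation of the linear model (400 runs, vs = 50) gave 6.0% with no extra components, 13.3% for r = 0.5 with ve = 0, and 2.3% for ve = 50, vsl = 5, s2 = 45. A random-intercept logistic model (500 runs) gave 3.2% with no extra components, 8.8 to 10.2% with a subject-by-lens SD of 1 to 3 logits, and 2.6% with an eye effect only.

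**Single-lens mean against theory.** By the same mean squares the planned model reports (vs + 0.5s2 + 0.7ve + 0.6vsl)/N; the truth is (vs + 0.5s2 + 0.5ve + vsl)/N. The subject variance is common to both and dilutes the error.
- vs = 25, ve = 0, vsl = 45, s2 = 5: 54.5 against 72.5; SE ratio 0.867; coverage 91.1%.
- vs = 25, ve = 50, vsl = 0, s2 = 50: 85 against 75; SE ratio 1.065; coverage 96.3%.

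For vs of 25 to 100, ve of 0 to 50 and r of 0 to 0.9, coverage stays at about 91 to 96%.

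**Wilson fallback.** For 120 eyes at 90% the interval is 83.3% to 94.2%. With inter-eye correlation 0.5 the design effect is 1 + 0.5 = 1.5, the effective number is 120/1.5 = 80, and the interval is 81.5% to 94.8%. Approximate coverage of the unadjusted interval: 2Φ(1.96/sqrt(1.5)) − 1 = 89%. At correlation 1 (effective number 60) it is 83%.

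**The case against.** The strongest reply is that the large type I errors belong to a contrast between two lenses, which is not what most of Section 11.5 tests. Sections 11.5.2 and 11.5.3 compare one lens's proportion or mean with a theoretical value, and hypothesis i compares a combination of two designs with one design on a binary outcome. This stands. A reader might infer that every test in Section 11.5 departs far from 5%; for hypotheses ii and iii the working does not support that, and for hypothesis i the linear figures do not carry over directly.

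It is also fair that direction and size are unknown and that the two omissions can cancel. But cancellation needs vsl = ve/2, and nothing in the protocol points to that value.

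A third reply is that covariance structure is commonly left to the SAP. That would answer a silent protocol. This one states the model three times, each time with one random term. A SAP could still add structure, and if it does the protocol text should be aligned.

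Fourth, extra random effects may not converge in the binary models, with two binary readings per subject-period and success near 90%. That stands and shapes the fix.

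Finally, a reader might add site to the charge, since Section 4.1 names "Two investigational sites in the UK" and no model has a site term. The documents do not support that as a width error. Each subject wears all lenses at one site, so an additive site shift goes into the subject effect and cancels from lens contrasts. For a lens mean it widens the interval. With the 30/30 numbering of Section 5.4, a fixed site term would leave the averaged lens mean, and any grading bias against theory, unchanged. Overlap, moreover, is measured from photographs or video rather than graded.

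**Conclusion.** The concern holds for the within-subject structure. As specified, the models cannot be relied on to give nominal error rates: the stated widths are right only if subject-by-lens variance happens to equal half the eye variance. The consequence is potentially material for between-lens contrasts, modest for single-lens means against theory, and one-directional for the Wilson fallback, whose intervals are too narrow whenever the two eyes are positively correlated.

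One should not conclude that the trial's intervals are known to be too narrow. That would require knowing the variance components, which the protocol does not report. The figures rest on assumed components, a balanced linear model and 60 completed subjects. The logistic simulations support the direction but show smaller departures than the most extreme linear cases.

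**What to change.** - **Section 11.5.3:** add random effects for eye within subject and for subject-by-period, or specify a structured 6 × 6 within-subject covariance.
- **Sections 11.5.1 and 11.5.2:** use a marginal logistic model with robust standard errors clustered on subject, or the same two random effects if they converge.
- **Fallback in both sections:** compute the Wilson interval with an effective sample size, number of eyes/(1 + inter-eye correlation), the correlation being estimated from the study data.

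No site term is needed for this purpose. The change affects the model statement only and needs no new data. Intervals may become somewhat wider. With a marginal model, lens odds ratios become population-averaged rather than subject-specific, which matches the proportion of eyes that Section 11.5.2 sets out to report.

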1 INTRODUCTION

Since ocular topographies vary within the population,¹ it is important that contact lens designs are selected that comfortably and successfully fit a wide range of eyes. Multiple designs generally give a wider coverage of the population than single designs. Because soft contact lenses are generally not available in a wide range of parameters, it is difficult to evaluate the effectiveness of design combinations. However, senofilcon A lenses have recently become available in multiple diameters, which offers the opportunity to explore the utility of various design combinations.

Computer modelling provides useful insights into the relationship between lens design and fit and allows an estimation of the fitting success rate for a given lens design on a given population.^{2,3} Recent calculations suggest that a combination of multiple diameter designs is likely to be more successful than multiple base curves of identical lens diameter.⁴

The main purpose of this study is to evaluate the fitting success of various combinations of senofilcon A lens designs. A secondary purpose will be to evaluate the validity of the Young soft contact lens fit model.²

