2.1 Hypotheses

The following hypotheses will be tested:

- i. The fitting success rate for a combination of two senofilcon A designs is greater than for a single design when fitted to a population skewed to larger corneas.
- ii. The fitting success rates for senofilcon A designs are equivalent to those predicted by the Young model.
- iii. The fitting characteristics (tightness, corneal overlap) for senofilcon A designs are equivalent to those predicted by the Young model.

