11.1 Sample Size Rationale

A sample size of 60 subjects showing a 90% success rate would give an 80% confidence interval of $\pm 5.0\%$. This would statistically differentiate success rates of 85% and 95%.

A sample size of 60 is sufficient to detect a mean difference of 5 (0-100) in tightness, or 0.2 mm in corneal overlap assuming the standard deviation of the mean differences in Table 2 below and assuming $\alpha=0.05$ with a power of 95%.

Table 2: Sample Size Justification:

	Sample Size	
	Tightness (0-100)	Corneal overlap (mm)
Mean of paired difference	5	0.2
SD of paired difference	10	0.4
Minimum sample size per group	42	42

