11.2 Level of Statistical Significance

The overall type I error rate will be preserved at 5%. To preserve type I error control, the study hypotheses will be evaluated using a sequential gate-keeping strategy. All tests will be two-sided. The three co-primary hypotheses will be simultaneously evaluated using $\alpha=0.05$, all of which must be met in order to satisfy the primary objective of this study.

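### Hypotheses ii and iii claim equivalence to the theoretical fit model and are co-primary, but the stated analysis does not test equivalence and the stated sample size is not shown to support it

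*Protocol*

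**What the plan says.** **Claim.** Protocol 2.1, hypothesis ii: "The fitting success rates for senofilcon A designs are equivalent to those predicted by" the theoretical model. Hypothesis iii: "The fitting characteristics (tightness, corneal overlap) for senofilcon A designs are equivalent to those predicted by" the same model.

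**Status.** Section 11.2 treats the three hypotheses as co-primary at a two-sided 0.05 level, "all of which must be met in order to satisfy the primary objective of this study". The Introduction gives the model a lower rank: "A secondary purpose will be to evaluate the validity of" the fit model.

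**Analysis.** For success rates, 11.5.2 fits a logistic mixed model with a Wilson fallback, obtains a 95% interval per lens type, and ends: "These confidence intervals will be compared to the theoretical success rates". For tightness and overlap, 11.5.3 fits linear mixed models and says: "Comparisons will be carried out using 95% confidence intervals constructed of least-square means (LSM) from the linear mixed models". The theoretical value appears only in the heading of 11.5.3.

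**Sizing.** Section 11.1 begins: "A sample size of 60 subjects showing a 90% success rate would give an 80% confidence interval of" ±5.0%, and adds: "This would statistically differentiate success rates of 85% and 95" per cent. It then justifies 60 subjects by the ability to detect a mean difference of 5 in tightness (SD 10) or 0.2 mm in overlap (SD 0.4). Section 5.1 plans about 50 subjects, range 40 to 60.

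**Scales.** The Synopsis lists the theoretical variables as edge strain in per cent (0-6% acceptable) and overlap in mm (0.2-1.2 mm acceptable). Appendix 5 measures tightness by push-up from 0 to 100%, with 50% optimum.

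**The concern.** An equivalence hypothesis is met when the data exclude every discrepancy large enough to matter. That takes a margin, and an interval for observed minus predicted that lies inside it. Neither 11.5.2 nor 11.5.3 does this, and 11.1 addresses a different question, namely whether a difference of a given size would be noticed.

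Because 11.2 requires all three hypotheses to be met, the primary objective hangs on two claims that the stated analysis does not decide. After the data are in, two people could apply the same text to the same intervals and disagree on whether the objective was met. An informal reading would also reward imprecision, since a wider interval contains the theoretical value more easily.

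Tightness has a further difficulty. The predicted and measured quantities are on different scales, and the protocol does not say how one is to be equated with the other.

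**Working it through.** **1. The precision figure in 11.1.** Inputs: rate 0.90, n = 60 (11.1). Half-width = z × √(p(1−p)/n).
- SE = √(0.90 × 0.10/60) = 0.0387.
- 80% confidence: 1.2816 × 0.0387 = 4.96 points. The stated ±5.0% is reproduced.
- 95% confidence, as used in 11.5.2: 1.96 × 0.0387 = 7.6 points.
- At n = 40, the lower planned size: SE = 0.0474, and 1.96 × 0.0474 = 9.3 points.

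**2. The difference-detection sizing in 11.1.** Inputs: difference/SD = 5/10 = 0.2/0.4 = 0.5. n = ((z for α + z for power)/0.5)².
- Two-sided 0.05, 95% power: ((1.960 + 1.645)/0.5)² = 51.98, so 52.
- Two-sided 0.05, 90% power: ((1.960 + 1.282)/0.5)² = 42.03, which fits the 42 in the table.
- The statement that 60 suffices is true (power 0.97), although the table's 42 does not go with 95% power. Either way, this is power to find a difference.

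**3. If an interval containing theory were counted as equivalence.** The protocol does not state this rule. The figures are conditional on it, on an assumed theoretical rate of 90% treated as a fixed constant, on an assumed true rate of 85%, on independent units, and on the Wilson interval (the fallback in 11.5.2, not the mixed model).
- n = 60: the 95% interval contains 90% for 50 to 58 successes. The binomial probability at a true rate of 85% is 0.72.
- n = 40: the interval contains 90% for 33 to 39 successes. The probability is 0.75.

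A prediction 5 points too high would pass about three times in four, and slightly more often in the smaller study.

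**4. What a proper equivalence rule would give for overlap.** Assumptions: margin 0.2 mm (a difference to detect in 11.1, not named there as a margin); SD 0.4 taken as the SD of measured minus predicted (11.1 does not say which pair it describes); one difference per subject; zero true difference. Rule: the 95% interval lies wholly inside ±0.2 mm. Normal approximation to power: 2Φ(0.2/SE − 1.96) − 1, with SE = 0.4/√n.

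| n | SE (mm) | Normal approximation | t-based |
|---|---|---|---|
| 40 | 0.0632 | 0.77 | 0.74 |
| 50 | 0.0566 | 0.88 | 0.87 |
| 60 | 0.0516 | 0.94 | 0.94 |

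With a true difference of 0.05 mm, the t-based values fall to 0.61/0.73/0.81. If each of the three lens types had to pass and results were independent, the zero-difference values cubed are about 0.40/0.66/0.82. Positive correlation between lens types would raise these.

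**5. Tightness.** No calculation is possible. Edge strain (0-6% acceptable) and push-up (0-100%, 50% optimum) share a percentage sign but not a scale, and no conversion is stated. The Synopsis ranges define a successful fit in the model; they are not equivalence margins.

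**The case against.** The strongest reply is that margins and decision rules often sit in the statistical analysis plan, which is not at hand, so their absence from the protocol is no defect. That is fair as far as it goes. But the protocol itself fixes the equivalence wording, the co-primary status, the form of the analysis and the basis of the sample size, and these do not fit together. A margin added later would not turn the 11.1 justification into one for equivalence.

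Three stronger readings are tempting and should not be drawn.

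- *The study cannot establish equivalence.* Step 4 shows otherwise for overlap: a single comparison has 0.94 power at 60 subjects with a 0.2 mm margin. What stands is that 11.1 does not show it.
- *The protocol will accept any interval that contains the prediction.* It says only that the intervals will be compared. Step 3 shows why that reading would be harmful, not that it was chosen.
- *The 85% versus 95% sentence sizes hypothesis ii by the wrong aim.* Section 11.1 does not tie it to a hypothesis. It may serve hypothesis i, where detecting a difference is the right aim. Only the tightness and overlap sentence clearly belongs to hypothesis iii.

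It can also be said that theory need not be a fixed constant: the model yields a yes/no prediction, and biometry is collected on every subject. If predictions are made on the same eyes, a paired comparison is possible and the Wilson figures would not describe it. That stands, and it is a reason to write the comparison down. For tightness, a link between edge strain and push-up might exist in the cited model paper, but the protocol does not invoke one.

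**Conclusion.** The concern holds as a mismatch between stated parts of the protocol: co-primary equivalence hypotheses, an analysis that does not test equivalence, and a sample size argued from detecting differences. This, and the disagreement between the Introduction and 11.2 on the rank of model validation, rest on the text alone.

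The precision shortfall is arithmetic on the plan's own inputs: ±5.0% becomes ±7.6 points at 60 subjects and ±9.3 at 40 once the 95% level of 11.5.2 is used. The pass probabilities of 0.72 and 0.75 are illustrative and hold only under the unwritten rule and assumptions in step 3. The overlap power depends on the assumed margin, on what SD 0.4 describes, and on how many lens types must pass.

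It must be fixed before analysis, because as written the protocol does not determine whether its primary objective has been met.

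**What to change.** - **Overlap (11.5.3).** Model measured minus predicted and declare equivalence only if the 95% interval lies wholly inside a justified margin; 0.2 mm is one candidate from the plan. State whether all three lens types must pass, and give joint power.
- **Success rate (11.5.2).** Apply the same rule with a justified margin, using a paired comparison if predictions are made on the same eyes. Otherwise reword hypothesis ii as estimation with 95% intervals.
- **Tightness (2.1 and 11.5.3).** Define a common scale for edge strain and push-up, with a margin, or reword this part of hypothesis iii as association or estimation.
- **Sizing (11.1).** Give equivalence power for the claims that remain, over the planned 40 to 60 subjects, and quote success-rate precision at 95%.
- **Status (11.2 and Introduction).** Agree on which hypotheses are confirmatory and limit the all-must-be-met rule to those.

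The cost is redrafting and a margin justification; no extra data or visits are needed. The real price is that hypothesis ii, and the tightness part of hypothesis iii, may have to leave the all-must-be-met rule.
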